	
Data analysis: The responses collected will be analyzed using a quantitative approach. Qualitative analyses will rely on thematic analysis assisted by Large Language Models (LLMs). These models will make it possible to automatically extract recurring themes, associated emotions, and nuances of perception in free-text responses, according to a standardized methodology developed by the investigators' team. The investigators have already successfully conducted this type of LLM-based thematic analysis (Raynaud et al, PsyArxiv 2025 https://osf.io/preprints/psyarxiv/pnx9e_v1).
 
Analyses will be conducted via commercial language-model APIs (Anthropic Claude, OpenAI ChatGPT, xAI Grok), justified by their superior performance for multilingual qualitative analysis. Only pseudonymized text responses will be transmitted, with no identifiers or sociodemographic data. Providers contractually guarantee zero data retention. Participants will be asked not to mention identifying information in their free-text responses (see the information notice in the appendix to this document).
 
To ensure reliability and scientific rigor, systematic manual verification will be performed on a representative subsample of responses. This independent review will make it possible to compare human and automated coding and refine the thematic categories.
 
Originality of the study: Unlike the vast majority of surveys conducted with patients, the questionnaire will contain only open-ended questions, giving each patient the opportunity to express themselves freely and in a nuanced way about their perceptions and feelings.
 
Such an approach, previously difficult to implement on a large scale, is now made possible by language models (LLMs), which are able to finely analyze large sets of textual responses.
 
This innovative methodology will provide a more faithful, precise, and human understanding of patients' perspectives, paving the way for a new generation of studies centered on patients' lived experience and voice.

Data collected (Justify the collection of sensitive/identifying data, if applicable)
	
 • Age • Sex • Year of the last transplant • Country of the last transplant • Transplant follow-up center • Transplant rank • Current occupation or last occupation held • Perceptions of the role of AI in medicine • Perceptions regarding a graft loss risk prediction system

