
Data flow (What happens to the data from extraction until deletion? Collection software, storage, security of storage media, access, partner recipients or subcontractors, retention period, etc.)
	
Data will be collected through the REDCap platform (HDS-certified hosting on Google Cloud, GDPR-compliant). The questionnaire is anonymous: no nominative data or identifiable medical data will be collected. Each participant will receive a unique link generating a non-traceable alphanumeric identifier.
 
The data flow is as follows:
 
Dissemination: Partner transplant centers and patient associations disseminate the REDCap link to eligible patients.
 
Collection: Participants complete the questionnaire anonymously via REDCap.
 
Export: Pseudonymized data are extracted (CSV format) by authorized members ([name], [name], [name]).
 
Storage: Files are stored in encrypted form on the secure PARCC INSERM U970 server, with access controlled by secure authentication.
 
Qualitative analysis by LLM: Only textual responses (without identifiers, sociodemographic data, or transplant-related information) are transmitted via secure API (HTTPS/TLS) to language-model providers (zero data retention). Results are returned to the PARCC INSERM server. Quantitative analyses are performed locally using R.
 
Archiving: 3 years in the active database, then 20 years in archives, under the responsibility of [name].
 
Fully anonymized datasets may be archived for secondary research purposes or scientific replicability.

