
Participant information (For example: recruitment during a consultation, or patients recontacted by mail, or call on social networks, etc. Attach the information notices planned for the different types of participants: adults, adolescents, children, legal guardians, etc. Justify the absence of an information
	
Participants will be contacted by email via their follow-up center, using the existing contact databases available in these centers.
 
The invitation message will briefly present the study and its sponsor, the Paris Institute for Transplantation and Organ Regeneration, as well as the responsible researchers.
 
It will also include an information notice specifying the objectives of the study, confidentiality arrangements, and a direct link to the online questionnaire hosted on REDCap.
 
Participation will be entirely voluntary, with no impact on medical follow-up or on the relationship with the transplant team.

notice, applicable.)	if	
Legal entity responsible for the project		INSERM
Natural person responsible for the project		[name]

Questionnaire: Perceptions of kidney transplant recipients about the role of Artificial Intelligence (AI) in healthcare and about a graft failure prediction system

1. Purpose of the study

You are invited to participate in a study aimed at better understanding how kidney transplant recipients perceive the use of a prediction system based on artificial intelligence (AI) that can predict the probability of graft loss (return to dialysis or retransplantation) over time. We also wish to gather patients' opinions on the future role of AI in medicine. The purpose of this study is to better understand how transplant recipients experience the arrival of new technologies such as artificial intelligence in their medical follow-up.

2. Consent Form

Your participation involves completing an anonymous questionnaire of approximately 15 to 20 minutes. No identifiable personal data will be collected. You may stop at any time, without justification.

By ticking the box below, you consent to participate in this study.

☐ Yes, I agree to participate in this study

☐ No, I do not wish to participate

3. Explanation of the prediction system

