The prediction system was developed to help physicians and patients assess the health of the kidney graft. It combines several clinical data points (kidney function, histological results, and immunological results) and predicts the percentage of risk that a patient will lose their graft over the next 10 years. The goal of this prediction system is to improve clinical decision-making, as well as the discussion between the physician and the patient.

A. Have you ever heard of this type of prediction system?

B. If yes, does your physician use such a prediction system in your post-transplant follow-up? Do you have access to the predictions?

4. Questions specific to the prediction system

- A. What do you think of the idea that an artificial intelligence such as this prediction system could predict your personal risk of graft loss?
- B. Do you find it useful for your physician to have access to this information? Why?
- C. Would you personally want to know your graft loss prediction?
- D. What fears or concerns do you have about AI being used to predict the outcome of your transplant?
- E. How could this information influence your daily life, for example your personal, family, professional choices, or your leisure activities?

5. General questions about artificial intelligence in healthcare

- A. In general, what do you think about the use of artificial intelligence in today's healthcare?
- B. What hopes or expectations do you have regarding AI in healthcare?
- C. What fears or reservations do you have regarding AI in healthcare?
- D. In your opinion, in what situations should or should not AI be used?
- E. Would you like to add any comments about your feelings regarding this prediction system or AI in medicine?

6. General information (demographics)

Age: _____ (years)

Sex: ☐ Female ☐ Male

Year of last transplant: _____

Country of transplant: _____

Transplant follow-up center: _____

Transplant rank: ☐ First ☐ Second ☐ Third or more

Current occupation or last occupation held: _____

7. Our thanks

Thank you for taking the time to share your perspective. Your responses will help us better understand the role that patients wish to give to artificial intelligence in the medicine of tomorrow. Your transplant center (or your patient association) will share the results of the study with you once the analyses are completed.

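### The survey is described to participants as anonymous, but its data are pseudonymized and indirectly identifying, and the promised exclusions are not assured for free text sent to language-model providers

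*Protocol*

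**What the plan says.** On anonymity, the Data flow section states "The questionnaire is anonymous: no nominative data or identifiable medical data will be collected" and "Each participant will receive a unique link generating a non-traceable alphanumeric identifier". The Consent Form (questionnaire section 2) tells participants "No identifiable personal data will be collected". The Type of study and Summary methodology entries also use the word anonymous.

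The Export step of the same Data flow section then says "Pseudonymized data are extracted (CSV format) by authorized members", and its closing line treats anonymized data as a separate, later product: "Fully anonymized datasets may be archived for secondary research purposes or scientific replicability". The Data collected entry and questionnaire section 6 list age in years, sex, year and country of last transplant, follow-up center, transplant rank and occupation, all per person. The Summary methodology also gives each participant a personal code for reopening the record until final validation.

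On the language models, the Data flow section states "Only textual responses (without identifiers, sociodemographic data, or transplant-related information) are transmitted via secure API (HTTPS/TLS) to language-model providers". The Data analysis paragraph describes the transmitted text as pseudonymized and excludes identifiers and sociodemographic data, but does not mention transplant information. Two safeguards are stated: providers guarantee by contract that they retain no data, and "Participants will be asked not to mention identifying information in their free-text responses".

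**The concern.** Two promises look stronger than the design.

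First, participants agree to take part on the statement that nothing identifiable is collected. The protocol's own terms for the working file say otherwise, and the items collected are the kind that single people out in combination. Participant Information says that centers will email patients from their existing contact databases, so there are parties who could match such attributes to a name.

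Second, the transfer sentence lists what will not reach commercial providers, while the open questions ask recipients about their graft, their follow-up and their lives. The Data flow section is meant to trace the data from extraction to deletion. It goes from export to storage to the API without a step that screens the text.

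At stake is the accuracy of what participants consent to, in a survey that itself asks about fears of AI in healthcare (items 4D and 5C). No estimate or sample size depends on it.

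**Working it through.** The protocol gives no figure for re-identification risk, so there is nothing to reproduce. The check has three parts.

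**1. The wording side by side.** Anonymous (Type of study, Summary methodology, Data flow, Consent Form) and pseudonymized (Data analysis, Data flow Export step) are applied to the same individual data. Because fully anonymized datasets are mentioned separately, the working file is not one of them on the protocol's own terms.

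**2. How identifying the collected items are.** Inputs from the Number of participants entry: 10,000 to 20,000 invited, with 10% to 15% responding. Expected respondents: 10,000 × 0.10 = 1,000 to 20,000 × 0.15 = 3,000. Three French centers have given preliminary agreement. The eventual number of centers is not given, so 3 and 20 are used as a range.

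Assumptions, none from the protocol: age mean 57, SD 14; 60% male; exponential time since transplant with mean 9 years; rank split 85/12/3%; centers of equal size. Records were simulated for all those invited, and a subset of the expected size was taken as respondents. Occupation and country were left out.

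| Centers | Invited / respondents | Unique among respondents, five items | Unique among all invited, five items | Unique among respondents, center and year only |
|---|---|---|---|---|
| 3 | 10,000 / 1,000 | 88% | 41% | 2% |
| 3 | 20,000 / 3,000 | about 70% | 27% | below 1% |
| 20 | 10,000 / 1,000 | 98% | 82% | 18% |
| 20 | 20,000 / 3,000 | 94% | 69% | 5% to 6% |

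The five items are age, sex, transplant year, center and rank. The column for all invited is the relevant one: someone unique among respondents may share the same values with a non-respondent, and 85% to 90% of those invited are expected not to respond. Adding occupation as 10 equal groups raises the 3-center figures to about 87% and 78%.

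A cruder check needs no simulation. With K equally likely combinations, the chance of being alone among N people is (1 − 1/K)^(N−1). Take 40 ages × 2 sexes × 15 years × 3 ranks × 3 centers, so K = 10,800. For N = 10,000 this gives (1 − 1/10,800)^9,999 = 0.40, and for N = 20,000 it gives (1 − 1/10,800)^19,999 = 0.16. The size depends on the assumptions, but it stays well above zero.

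**3. What the free text can contain.** Item 3B asks about the physician's practice in the respondent's follow-up, 4A about personal risk of graft loss, and 4D about the outcome of the transplant. Item 4E asks "How could this information influence your daily life, for example your personal, family, professional choices, or your leisure activities". A direct answer to 3B, 4A or 4D is itself about the respondent's transplant, so the transplant exclusion cannot hold literally for content. For other excluded content, let q be the assumed share of respondents who disclose some. With q = 0.1%, 1,000 × 0.001 = 1 to 3,000 × 0.001 = 3 such records are expected. The chance of at least one is 1 − 0.999^1,000 = 63% to 1 − 0.999^3,000 = 95%. With q = 1%, 10 to 30 are expected.

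**The case against.** The transfer sentence can be read as a rule about fields. Its excluded categories match the structured items in questionnaire section 6, and on that reading nothing contradicts it. Nowhere does the protocol say that the text is unredacted; it calls the text pseudonymized without saying how. The open items seek opinions and do not ask for a name, hospital, date or job title. Zero retention and the request to respondents are real safeguards, the return code works only until final validation, and the working file is encrypted with controlled access.

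Most of this stands. A reader might infer that the transfer sentence is simply untrue; the documents do not show that for identifiers or sociodemographic data. What survives is narrower. Zero retention acts after transfer, the request relies on compliance and covers only identifying information, and no described step removes content before the API call.

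A reader might also infer that anyone who knows a patient's center and transplant year could find that person in a shared dataset. The check does not support this: those two items alone single out only about 0.2% to 18% of respondents. The protocol also reserves secondary archiving for fully anonymized data, although it does not say how the file would become so.

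Finally, a reader might infer that participants are never told about commercial AI processing. The information notice is not shown, so this cannot be judged.

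**Conclusion.** The anonymity point holds. The current text contradicts itself, and the consent sentence claims a property that the file lacks. About 27% to 41% of respondents with 3 centers, or 69% to 82% with 20, would be unique among all those invited on five collected items, before occupation is used. These figures rest on assumed distributions; the contradiction in wording does not. Uniqueness also describes the data, not the probability that anyone attempts or achieves a match.

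The language-model point holds in limited form. The exclusion is defensible for structured fields, not assured for free-text content, and not literally achievable for transplant-related content. Both should be corrected before distribution, since this document carries the consent and data-flow wording.

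**What to change.** 1. In the Consent Form, and in the Type of study, Summary methodology and Data flow entries, replace the claims of anonymity and of no identifiable data with wording such as: *pseudonymized; no names or contact details are collected*.
2. Before any API call, run a local automated screen in both languages that masks direct identifiers in the text (names, hospitals, places, dates). Leave family and occupational content in place, since item 4E is meant to elicit it. Reword the Data flow sentence to say that the structured sociodemographic and transplant fields are withheld and that residual personal details may remain in the text.
3. State what turns the working file into a fully anonymized archive: band age and transplant year, coarsen center and occupation, and screen the free text.

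The cost is one local script, recoding before archiving, a slight loss of context where words are masked, and a less reassuring consent sentence. The working analysis file keeps its full detail.

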Study background (with bibliographic references)	
Kidney transplantation is currently the reference treatment for end-stage kidney disease, with more than 170,000 transplants performed worldwide each year (Global Observatory on Donation and Transplantation, 2024). Despite major progress in short-term survival, long-term graft survival remains limited: approximately 40% of patients return to dialysis within 10 to 15 years after transplantation (Hart et al, AJT 2019, PMID 30838768).
 
In recent years, artificial intelligence (AI) has emerged as a promising tool to predict graft outcomes and support clinical decision-making (Raynaud et al, Lancet Digital Health 2021 PMID 34756569; Loupy et al, Nature Medicine 2025 PMID 40659768). The iBox system, developed by the Paris Institute for Transplantation and Organ Regeneration, makes it possible to calculate a personalized probability of graft loss up to ten years after the evaluation of a kidney transplant recipient.
 
This algorithm has been internationally validated in several cohorts and clinical trials (Lombardi et al, AJT 2025, PMID 39674514; Truchot et al, JASN 2025, PMID 40168162), performs better than clinicians in predicting risk (Divard et al, Communications Medicine 2022, PMID 36418380), and was qualified by the European Medicines Agency as an endpoint for clinical trials in 2022.
 
However, although the clinical value of iBox and similar predictive tools is well documented, how patients perceive them remains largely unexplored.
 
Understanding how kidney transplant recipients perceive the prediction of their individual risk of graft loss (in terms of usefulness, acceptability, fears, or impact on daily life), as well as their broader views on the role of artificial intelligence in medicine, including their hopes, expectations, and concerns regarding its deployment, is essential to ensure implementation that is ethical, transparent, and truly patient-centered (Young et al, Lancet Digital Health 2021, PMID 34446266).

Primary objective and corresponding endpoints (Please specify the longer-term application of the study if necessary)	This study therefore aims to explore the perceptions, expectations, and concerns of kidney transplant recipients regarding the use of artificial intelligence, and to assess their specific perceptions of the use of a graft loss risk prediction system, through an open-ended questionnaire distributed on a large scale in France and the United States.

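### The institute that built iBox is presented to patients as the survey's sponsor, partly through their own center, and no shown text says that critical answers are equally welcome or hidden from the transplant team

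*Protocol*

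**What the plan says.** **Who made the tool and who sponsors the survey.** The Study background section reads: "The iBox system, developed by the Paris Institute for Transplantation and Organ Regeneration". Under Participant information: "The invitation message will briefly present the study and its sponsor, the Paris Institute for Transplantation and Organ Regeneration".

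**How patients are reached.** Participant information describes one route: "Participants will be contacted by email via their follow-up center, using the existing contact databases available in these centers". The Data flow section gives two: "Partner transplant centers and patient associations disseminate the REDCap link to eligible patients". The Summary methodology also counts patient associations among the channels and reports preliminary agreement from three French centers and five associations.

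**How the tool is introduced.** Questionnaire section 3 opens: "The prediction system was developed to help physicians and patients assess the health of the kidney graft". It then lists the inputs, the 10-year risk output and the intended gains for decisions and for discussion with the physician. It mentions no limits or errors.

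**What is asked.** Item 4A asks for an opinion of the idea, 4B whether the physician's access to the prediction is useful, and 4C whether the respondent would want to know the result. Item 4D asks about fears over the prediction, 5C about reservations on AI in healthcare, and 5D about where AI should and should not be used. Section 6 has a field for the follow-up center.

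**What reassurance is given.** The consent text says that the questionnaire is anonymous and can be stopped at any time. Participant information says that taking part is voluntary and does not affect care, and that the information notice covers confidentiality.

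**How answers are coded.** Themes are extracted with language models, using a method from the investigators' own team. A representative subsample is checked by hand: "This independent review will make it possible to compare human and automated coding and refine the thematic categories".

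**The concern.** The primary objective is to learn how recipients perceive AI and, specifically, a graft-loss prediction system. The background lists usefulness, acceptability and fears among the perceptions of interest. Here the developer of one such system is measuring opinion of that class of tool, in part through the team that cares for the respondent.

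A patient who receives the request from their own center, reads a description limited to benefits, and is asked whether the tool would help their physician may give a courteous answer. The expected direction for 4A to 4C is favourable. Such a lean would be systematic, would look like a finding, and could not be removed once the answers are in. A reader of a favourable result would be likely to raise the objection, and the cheap time to meet it is before the questionnaire goes out.

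**Working it through.** The Protocol gives no figure for this effect, so the check sets its sections side by side.

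1. **Developer and sponsor.** Study background and Participant information name the same institute. This link is established.
2. **Sender.** Participant information has the center sending the email. Summary methodology and Data flow add patient associations. The sender effect therefore applies to part of the sample, and the Protocol does not say how large a part.
3. **Description of the tool.** Section 3 gives purpose, inputs, output and intended benefits, with nothing on limits. This is established.
4. **Invitation to criticise.** Items 4D, 5C and 5D ask for it directly. What is missing from the shown text is a statement, before 4A to 4C, that unfavourable answers are as welcome as favourable ones.
5. **Who sees the answers.** The consent text promises anonymity. The no-impact assurance concerns participation, not what is written. In Data flow, centers only pass on the link, and authorized members export the data to an INSERM server. The shown text addressed to patients does not tell them that their transplant team will not read individual answers. The information notice is not shown and may say so.
6. **Coding.** The manual review is described as independent, but the Protocol does not say who does it or what they are independent of.

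**Why sample size does not help.** The planned invitations and response rates imply 10,000 × 0.10 = 1,000 to 20,000 × 0.15 = 3,000 responses. The 95% half-width for a proportion near one half is 1.96 × √(0.25/n):

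- n = 1,000: 1.96 × √(0.25/1,000) = 0.031, or 3.1 points
- n = 3,000: 1.96 × √(0.25/3,000) = 0.018, or 1.8 points

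Sampling error shrinks as responses accrue. If a fraction s of those who hold a concern leave it out, a true share p is reported as p × (1 − s), and n does not appear in that expression. The Protocol gives no value for s, so the shift itself cannot be computed.

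**The case against.** **The questionnaire does ask for criticism.** A reader might infer that nothing invites critical views. Items 4D, 5C and 5D contradict that, and 4D even presupposes concerns. This part of the objection stands in full. What remains is narrower: asking about fears in 4D does not remove courtesy from 4A to 4C, which come before it.

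**Most respondents may not connect the sponsor with the tool.** The questionnaire names neither iBox nor its developer, and the invitation as described is not said to reveal the developer role. This weakens the sponsor effect considerably. It also means that announcing the role before patients answer could create the very cue one wants to avoid.

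**The center's part is limited.** Associations are a second channel, answers are anonymous, and centers have no stated access to responses. The field for the follow-up center comes after the opinion questions, and nothing says it is compulsory. All of this stands. Set against it, anonymity may feel weaker to someone asked for their center together with age, sex, occupation, transplant year and transplant rank.

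**The coding point is mostly missing detail.** Who codes is commonly settled in an analysis plan, which is not shown. The Protocol credits iBox to an institute, not to identified coders, so a reader who infers that people with a stake in the tool will refine the themes goes beyond the text.

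**There is no contradiction over the sponsor.** A reader might see a second sponsor in INSERM. It fills a different field, "Legal entity responsible for the project", and is never called sponsor.

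**Conclusion.** The point holds as a modest, inexpensive improvement to the instrument; it is not an error in the plan. The developer of iBox is the sponsor named to patients, the tool is described by its benefits alone, and the shown text neither welcomes critical answers explicitly nor tells respondents that their transplant team will not see what they write. Items 4A to 4C may lean favourable as a result.

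The size is unknown. A reader might try to supply one, for example by assuming that 5% to 10% of those with a concern omit it, so that a theme held by 40% is reported at 40% × 0.95 = 38% to 40% × 0.90 = 36%. Nothing in the Protocol supports such a rate. Even on that assumption, the 2-point end lies below the 3.1-point half-width at 1,000 responses, so it would not show that the lean outweighs sampling error.

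The conclusion rests on two assumptions: that the information notice, which is not shown, does not already contain these statements, and that some respondents are sensitive to sender and framing.

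**What to change.** 1. Before launch, add at the head of questionnaire section 4, in both languages: *Favourable and critical opinions are equally useful to us. Your transplant team will not see your individual answers.* Keep the second sentence only if the access described under Data flow makes it true. The names of the authorized members are removed from the text at hand, so the sponsor must confirm that none belongs to a participating transplant team.
2. Where existing study members allow, assign the manual review already planned under Data analysis to members with no role in developing iBox, and say so. This changes who does the work without adding any.
3. Declare in the publication that the sponsoring institute developed iBox. Placing this in the publication keeps it from acting as a cue while patients answer.

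The cost is two sentences of questionnaire text and one staffing decision. The downsides are a slightly longer questionnaire and fewer iBox experts in the coding check.

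### Item 3B puts two questions in one and item 4C asks for no reason, so one-word replies lose information that cannot be recovered after collection

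*Protocol*

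**What the plan says.** The Originality paragraph of the summary methodology declares that "the questionnaire will contain only open-ended questions, giving each patient the opportunity to express themselves freely". The Data analysis paragraph says that "The responses collected will be analyzed using a quantitative approach". It adds LLM-assisted thematic analysis of the free text, with manual verification on a representative subsample.

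The questionnaire appended to the protocol contains these items:

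- **3A:** "Have you ever heard of this type of prediction system"
- **3B:** "If yes, does your physician use such a prediction system in your post-transplant follow-up? Do you have access to the predictions"
- **4B:** "Do you find it useful for your physician to have access to this information? Why"
- **4C:** "Would you personally want to know your graft loss prediction"

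The form shows tick boxes for consent, sex and transplant rank, and none in sections 3 to 5. The Data flow section describes the questionnaire as anonymous, with an identifier that cannot be traced back. The Study period field places distribution in May 2026.

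**The concern.** An open-ended survey depends on questions that invite explanation. 4C can be answered in full with one word and, unlike 4B, does not ask why. Yet a patient's wish to know, or not to know, the personal prediction bears directly on acceptability, which the Study background names among the perceptions to be understood.

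Item 3B has a different fault. Use by the physician and access by the patient are separate facts. A patient may be followed with such a system without seeing its output, or may not know what the physician uses. When both are asked under one letter, a short reply does not show which one it answers.

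At stake are the reasons behind 4C and a usable record of prior use and access. Both are lost when the form is filled in, before any analysis begins.

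**Working it through.** The protocol gives no precision target, expected proportion or coding accuracy, so there is no stated figure to reproduce. The main check is a reading of the items.

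**Item 3B: what a one-word reply can mean**

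| Reply | Compatible situations |
|---|---|
| Bare 'yes' | Physician uses it and patient has access; or physician uses it and the access part was not answered |
| Bare 'no' | Physician does not use it, so access hardly arises; or physician uses it but patient has no access, and only the last question was answered |
| 'Do not know' | Unknown use; or unknown access |

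Each reply fits at least two situations. The bare 'yes' is the more ambiguous of the first two, but the bare 'no' is not safe either.

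**Items 4B and 4C side by side.** Both open with a closed question. 4B then asks why; 4C does not. The form therefore already has the device that 4C lacks.

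**Can the loss be repaired later?** Manual verification compares human with automated coding of the same text. If the text is one word, a human reader has no more information than the model. Respondents may revise their answers before final validation, but nothing in the plan prompts them to clarify. With a non-traceable identifier, the plan has no route back to them.

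**Scale for 3B**

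- Implied responses: 10,000 × 0.10 = 1,000 to 20,000 × 0.15 = 3,000 (Number of participants field).
- 3B applies only to those who answer yes to 3A, a share the protocol does not give. If it were 10% to 30% (assumption), 3B would concern 1,000 × 0.10 = 100 to 3,000 × 0.30 = 900 people.
- The fraction of these who would give a one-word reply is unknown.

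**Coding error, if a proportion were reported from free text**

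Reported proportion = Se × p + (1 − Sp) × (1 − p), with sensitivity Se and specificity Sp both assumed. At a true p = 0.80:

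| Se = Sp | Reported proportion | Bias (points) |
|---|---|---|
| 0.99 | 0.792 + 0.002 = 0.794 | −0.6 |
| 0.98 | 0.784 + 0.004 = 0.788 | −1.2 |
| 0.95 | 0.760 + 0.010 = 0.770 | −3.0 |
| 0.90 | 0.720 + 0.020 = 0.740 | −6.0 |

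At p = 0.50 with Se = Sp the bias is zero. For comparison, the 95% sampling half-width at p = 0.80 is 1.96 × √(0.80 × 0.20 / n), which is 2.5 points at n = 1,000 and 1.4 points at n = 3,000. Coding error could thus be well below or well above sampling error, and the protocol does not settle which.

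**The case against.** The best defence is that free text is a declared and reasoned design choice. The objective is exploratory, the secondary objectives field is empty, and no proportion is named as an endpoint. Items 3A and 3B stand under the explanation of the system, which suggests context rather than outcome. A free-text field also lets respondents answer both parts of 3B and volunteer reasons at 4C. The form was tested with six recipients to refine its wording, and human verification of the coding is planned.

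Much of this stands. A reader might infer that the study's main proportions will be biased by coding error, say by 3 points, and that every perception item needs a tick box. The documents do not support that:

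- They name no main proportion.
- They do not say how yes/no content will be coded.
- The 3-point figure depends on one assumed accuracy and one assumed true value. A bare yes or no is also the easiest text to code, so an accuracy as low as 0.95 is least plausible there.
- Tick boxes ahead of the perception items would trade away part of the chosen design and might frame the text that follows.

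What the defence does not answer is narrower. That respondents can elaborate does not mean they will, and neither 3B nor 4C asks them to. The planned verification addresses coding, not missing content.

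**Conclusion.** The point holds for two items. 3B combines two questions, so a one-word reply cannot be reliably assigned. 4C is closed and asks for no reason, which conflicts with the claim that all questions are open-ended. 3A is also closed in wording, but as a factual filter it does less harm.

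The loss is permanent once the form is out. Its size is not derivable from the protocol, because neither the share of patients who have heard of such systems nor the share of one-word replies is given. No bias in any study estimate is claimed.

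The conclusion assumes that the REDCap form matches the printed questionnaire, with one field for 3B and free text for 4C. The field types are not shown. If REDCap already has separate fields for the two parts of 3B, that half of the point falls away.

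**What to change.** Before distribution:

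1. Split 3B into 3B1, whether the physician uses such a system (allowing 'do not know'), and 3B2, whether the patient has access to the predictions.
2. Add 'Why or why not?' to 4C.

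Both changes fit within the open-ended design. They cost one extra item and a short recheck of the French-English wording, since the reworded items fall outside the testing already done.

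Optionally, if the sponsor intends to report proportions for the factual items 3A and 3B, give those items Yes / No / Do not know fields and describe the questionnaire as mainly, rather than only, open-ended. The perception items can stay as free text.
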